4.1.4 Other imputations

Incomplete assessment dates for tumor assessment

All investigation dates (e.g., MRI scan, CT scan) must be completed with day, month and year. If one or more assessment dates are incomplete but other investigation dates are available, the incomplete date(s) are not considered for calculation of the assessment date and assessment date is calculated as the latest of all investigation dates (e.g., MRI scan, CT-scan) if the overall lesion response at that assessment is CR/PR/SD/NE. Otherwise – if overall response is progression – the assessment date is calculated as the earliest date of all investigation dates at that evaluation. If all measurement dates have no day recorded, the 1st of the month is used. If the month is not completed, for any of the investigations, the respective assessment will be considered to be at the date which is exactly between the previous and the following assessment. If a previous and following assessment is not available, this assessment will not be used for any calculation.

Incomplete death date or last known participant alive date from survival eCRF page

For rare cases when either day is missing or both month and day are missing for the date of death, the following partial imputation rules will be implemented:

- If only day is missing, then impute the last known participant alive date (from “Survival” eCRF) or death date with max[(01MONYYYY), any valid date used for deriving last contact date + 1].
- If both day and month are missing, then impute the last known participant alive date or death date with max[01JANYYYY, any valid date used for deriving last contact date + 1].

4.2 AEs coding/grading

AEs will be coded using the Medical dictionary for regulatory activities (MedDRA) using the latest version available prior to clinical database lock and will be graded using the Common Terminology Criteria for Adverse Events (CTCAE) version 5.0.

4.3 Laboratory parameters derivations

Grade categorization of lab values will be assigned programmatically as per CTCAE version 5.0. The calculation of CTCAE grades will be based on the observed laboratory values only, clinical assessments will not be taken into account. The criteria to assign CTCAE grades are given in a Novartis internal document for CTCAE grading of laboratory parameters. The latest available version of the document based on the underlying CTCAE version 5.0 at the time of analysis will be used. For laboratory tests where grades are not defined by CTCAE version 5.0, results will be graded by the low/normal/high classifications based on laboratory normal ranges.

A severity grade of 0 will be assigned for all non-missing lab values not graded as 1 or higher. Grade 5 will not be used. For laboratory tests that are graded for both low and high values, summaries will be done separately and labelled by direction, e.g., sodium will be summarized as hyponatremia and hypernatremia.

4.3.1 Grading imputation rules

CTC grading for blood differentials is based on absolute values. However, this data may not be reported as absolute counts but rather as percentage of WBC.

If laboratory values are provided as “< X” (i.e. below limit of detection) or “> X”, prior to conversion of laboratory values to SI unit, these numeric values are set to X.

The following rules will be applied to derive the WBC differential counts when only percentages are available for a certain differential, “xxx”

$$\text{xxx count} = (\text{WBC count}) \times (\text{xxx \%value} / 100)$$

Further derivation of laboratory parameters might be required for CTCAE grading. For instance, corrected calcium can be derived using the reported total calcium value and albumin at the same assessment using the following formula:

Corrected Calcium (mg/dL) = Calcium (mg/dL) – 0.8 [Albumin (g/dL) – 4]

In order to apply the above formula, albumin values in g/L will be converted to g/dL (by multiplying by 0.1), calcium values in mmol/L will be converted to mg/dL (by dividing by 0.2495). For calculation of laboratory CTC grades 0 and 1, the normal range for derived corrected calcium is set to the same limits (in mg/dL) as for calcium.

CTC grades for the derived absolute WBC differential counts (neutrophils, lymphocytes) and corrected calcium will be assigned as described above for grading.

4.4 Statistical models

4.4.1 Analysis supporting primary objective(s)

Confidence interval for overall response rate and disease control rate

Responses will be summarized in terms of percentage rates with a $100(1 - \alpha)\%$ confidence interval using an exact binomial approach (implemented using SAS procedure FREQ with EXACT statement for one-way tables ([Clopper, Pearson 1934](#))).

4.4.2 Analysis supporting secondary objective(s)

Kaplan-Meier estimates

For time-to-event endpoints (DOR, PFS, OS), an estimate of the survival function will be constructed using the Kaplan-Meier (product-limit) method as implemented in SAS PROC LIFETEST with METHOD=KM option. The PROC LIFETEST statement will use the option CONFTYPE=LOGLOG.

Median survival will be obtained along with the 95% confidence interval calculated from PROC LIFETEST output using the method of ([Brookmeyer, Crowley 1982](#)). Kaplan-Meier estimates of the survival function with 95% confidence intervals at specific time points will be summarized. The standard error of the Kaplan-Meier estimate will be calculated using Greenwood's formula ([Collett 1994](#)).

4.5 Determination of missing adequate assessments

The term "missing adequate tumor assessment" is defined as a tumor assessment not done or a tumor assessment with overall lesion response "NE". For the sake of simplicity, a "missing adequate tumor assessment" will also be referred to as a "missing assessment".

As described in Appendix 8 (Section 10.8) of the clinical study protocol, the PFS censoring and event date options depend on the presence and the number of missing tumor assessments (TAs). In the analysis of PFS, an event occurring after two or more missing assessments is censored at the last adequate tumor assessment, i.e. the last assessment preceding the missing assessment(s).

An exact rule to determine whether there is no, one or two missing TAs is therefore needed. This rule is based:

- On the time interval between the last adequate tumor assessment (LATA) date and the event date
- On the time interval between the last adequate tumor assessment date and the cut-off date

In this study, the protocol defined schedule of assessments is

- Every 6 weeks during the first 54 weeks (i.e. at week 6, 12, 18, 24, 30, 36, 42, 48, 54)
- Every 12 weeks thereafter (i.e. at weeks 66, 78, 90, etc.) until confirmed PD

The scheduled date of tumor assessments (in weeks from start of treatment), protocol-specified windows for tumor assessments (\pm 7 days/1 week), and the thresholds for LATA to belong to a visit can be found in the following [Table 5-4](#).

Table 5-4 Schedule for tumor assessment and time windows

Assessment schedule		Scheduled date - 1 week	Scheduled date (weeks from start of treatment)	Scheduled date + 1 week	Threshold (weeks)*
Every 6 weeks for the first 54 weeks	Baseline	0	0 [#]	1	N/A
	C3D1	5	6	7	9
	C5D1	11	12	13	15
	C7D1	17	18	19	21
	C9D1	23	24	25	27
	C11D1	29	30	31	33
	C13D1	35	36	37	39
	C15D1	41	42	43	45
	C17D1	47	48	49	51
	C19D1	53	54	55	60
Every 12 weeks thereafter	C23D1	65	66	67	72
	C27D1	77	78	79	...
...					

* The threshold corresponds to the mid-point between the current and next visit (except for baseline) and to the upper limit for LATA to be matched to a certain scheduled assessment. e.g. if LATA is at week 10, this is after threshold for C3D1 and before that for C5D1, so the matching scheduled assessment is C5D1.

Day of start of treatment is taken as 0.

To calculate the number of missing tumor assessments, the LATA before an event is matched with a scheduled tumor assessment using the time window in the table above (essentially whichever scheduled assessment it is closest to).

D1 and D2 are calculated for that scheduled assessment based on the protocol-specified schedule and windows.

- The threshold D1 is defined as the protocol-specified time interval between the TAs plus $2 \times$ the protocol-allowed time window around the assessments (i.e. $= 2 \times 1$ week = 2 weeks).
- The threshold D2 is defined as twice the protocol-specified time interval between the TAs plus $2 \times$ the protocol-allowed time window around the assessments (except when the matched scheduled tumor assessment is from C15D1 to C19D1 in which case D2 is defined in Rule 2).

Since there is a change of schedule for tumor assessments after first 54 weeks, D1 and D2 are defined differently depending on when LATA occurs:

- Rule 1: if LATA happens within 45 weeks of start of treatment, the matched scheduled tumor assessment is C15D1, D1 = 6+2 = 8 weeks and D2 = $6 \times 2 + 2 = 14$ weeks.
- Rule 2: if LATA happens after 45 weeks from start of treatment, the matched scheduled tumor assessment is C15D1 or after, but within 51 weeks (the matched scheduled tumor assessment is C17D1), D1 = 6+2 = 8 weeks and D2 = $6+12+2 = 20$ weeks.
- Rule 3: if LATA happens after 51 weeks from start of treatment (the matched scheduled tumor assessment is C17D1), D1 = 12+2 = 14 weeks and D2 = $12 \times 2 + 2 = 26$ weeks.

The number of missing events is defined as:

- An event after LATA+D1 weeks will be considered as having ≥ 1 missing assessment
- An event after LATA+D2 weeks will be considered as having ≥ 2 missing assessments

The same definition of D2 will be used to determine the PFS censoring reason. If there is no post-baseline adequate tumor assessment available (before an event or a censoring reason occurred), the start of treatment date will be used to compute the interval.

If the time interval between the LATA date and the earliest of the following dates:

- Analysis cut-off date
- Date of consent withdrawal
- Date of start of new anticancer therapy
- Date of study treatment discontinuation due to lost to follow-up or date of end of post-treatment efficacy follow-up discontinuation due to lost to follow-up

is less or equal to D2, then the PFS censoring reason will be respectively:

- Ongoing without event
- Withdrew consent
- New anticancer therapy given prior to protocol defined progression
- Lost to follow-up

However, if the time interval is larger than D2 with no event, then the PFS censoring reason will always default to “Adequate assessment no longer available”. If the time interval between the last adequate tumor assessment date and the PFS event date is larger than D2, then the participant will be censored, and the censoring reason will be “Event documented after two or more missing tumor assessments”.

No baseline tumor assessment

Since the timing of disease progression cannot be determined for participants with missing baseline tumor assessment, these participants are censored in the PFS analysis at the date of start of treatment. This only applies to the “progressive disease” component of the PFS assessment. Participants without any baseline tumor assessment who die within the D2 time interval from the date of start of treatment will be counted as having an event in at the date of death.

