8.4.1 Tumor assessment

Tumor response will be assessed both locally and centrally according to the Novartis guideline version 3.2 (Appendix 8 Section 10.8) based on RECIST 1.1 (Eisenhauer et al 2009).

The central review of the scans will be carried out in a blinded fashion. Imaging data will be centrally collected and checked for quality by an imaging Contract Research Organization (CRO) designated by Novartis (Details of the central review process will be described in the independent review charter).

Information regarding biopsy results, prior interventions (e.g., radiotherapy), pre-existing radiographic findings that mimic metastatic disease at baseline/screening and prior interventions should be transmitted to the imaging CRO with the baseline images for review by

the independent radiologist. Sites must transfer information as specified in the imaging CRO site manual and ensure the data is consistent with the data entered in the clinical database.

The CT scan component of the FDG-PET/CT should be used for treatment response assessment only if the CT is of similar diagnostic quality as a CT performed without PET, including the utilization of i.v. contrast media. At the discretion of the Investigators, FDG-PET scans may be performed to document progressive disease per RECIST 1.1 (Section 10.8).

The imaging assessment collection plan is presented in Table 8-1.

Table 8-1 Imaging Assessment Collection Plan

Procedure	Screening/Baseline (within 28 days prior to start of treatment)	During Treatment/Follow-up
Chest, abdomen and pelvis CT or MRI (with intravenous contrast enhancement)#	Mandated	During Treatment: Mandated, every 6 weeks (+/- 7 days) from C1D1 until Week 54, then every 12 weeks (+/- 7 days) until confirmed PD* During Post Treatment Follow-Up: participants with EOT reason other than disease progression, withdrawal of consent/opposition to use data/biological samples or death will continue to collect imaging and follow the same schedule of every 6 weeks (+/- 7 days) for the 54 weeks after C1D1, then every 12 weeks (+/- 7 days), thereafter until confirmed PD*

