Refer to [Table 2-5](#) for censoring and event date options and outcomes for DOR. The same principles also apply for PFS.

Table 2-6 Outcome and event/censor dates for DOR and PFS analysis

Situation	Date	Outcome
No baseline assessment	Date of start of treatment*	Censored
Progression or death at or before next scheduled assessment	Date of progression (or death)	Progressed
Progression or death after exactly one missing assessment	Date of progression (or death)	Progressed
Progression or death after two or more missing assessments	Date of last adequate assessment prior to missed assessment	Censored
No progression (or death)	Date of last adequate assessment	Censored
Treatment discontinuation due to “Disease progression” without documented progression, i.e., clinical progression based on investigator claim	Ignore the new anticancer therapy and follow situations above	As per above situations
New anticancer therapy given prior to protocol defined progression	Date of last adequate assessment prior to start of new anticancer therapy	Censored
Death before first PD assessment	Date of death	Progressed

*The rare exception to this is if the participant dies no later than the time of the second scheduled assessment as defined in the protocol in which case this is a PFS event at the date of death

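### SAP 4.5 gives conflicting D2 limits for PFS at C15D1, C17D1 and C19D1; the stated exception would censor an on-schedule week-78 progression after a single missed scan

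*SAP*

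**What the plan says.** SAP 4.5 counts missed scans from the gap between the last adequate tumor assessment (LATA) and the event. The LATA is matched to a scheduled visit through Table 5-4, whose footnote reads "The threshold corresponds to the mid-point between the current and next visit (except for baseline". The upper limits are week 45 for C15D1, week 51 for C17D1 and week 60 for C19D1. An event later than LATA + D2 is treated as following at least two missed scans and is censored. D2 also determines the PFS censoring reason.

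D2 is defined in general as two scan intervals plus two windows, "except when the matched scheduled tumor assessment is from C15D1 to C19D1 in which case D2 is defined in Rule 2". Three rules follow:

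- Rule 1: "if LATA happens within 45 weeks of start of treatment, the matched scheduled tumor assessment is C15D1"; D1/D2 are 8/14 weeks.
- Rule 2: LATA after week 45 and within week 51, with the visit described both as C15D1 or later and as C17D1; D1/D2 are 8/20 weeks.
- "Rule 3: if LATA happens after 51 weeks from start of treatment (the matched scheduled tumor assessment is C17D1"; D1/D2 are 14/26 weeks.

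Table 2-6 (SAP 2.7.4) has a row for "Progression or death after exactly one missing assessment", which counts as an event. After two or more missing assessments, the participant is censored at the last adequate one.

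**The concern.** The section is meant to supply an exact counting rule, yet it gives two D2 values for each of three visits. C15D1 has 14 weeks (Rule 1) or 20 (exception). C17D1 has 20 (Rule 2) or 26 (Rule 3's label). C19D1 has 26 (Rule 3's week range) or 20 (exception).

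A program keyed to visit names and one keyed to weeks would therefore assign different PFS statuses to the same participant. A true event could become a censored time months earlier, or an event that Table 2-6 excludes could be kept. In an open-label single-arm trial, that choice should not be left until the data have been seen.

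**Working it through.** **Inputs.** Scan weeks, from SAP 4.5: "Every 6 weeks during the first 54 weeks (i.e. at week 6, 12, 18, 24, 30, 36, 42, 48, 54" and "Every 12 weeks thereafter (i.e. at weeks 66, 78, 90, etc.) until confirmed PD". Protocol 8.4.1 (Table 8-1) agrees: "Mandated, every 6 weeks (+/- 7 days) from C1D1 until Week 54, then every 12 weeks (+/- 7 days) until confirmed PD". The relevant weeks are 42, 48, 54, 66 and 78. The window is ±1 week, so two windows are 2 weeks.

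**The plan's own figures.** Rule 1: 6 + 2 = 8 and 6 × 2 + 2 = 14. Rule 2: 6 + 2 = 8 and 6 + 12 + 2 = 20. Rule 3: 12 + 2 = 14 and 12 × 2 + 2 = 26. All reproduce.

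**D1 and D2 from the schedule.** D1 = next scan − matched scan + 2. D2 = second next scan − matched scan + 2.

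- C15D1 (week 42): D1 = 48 − 42 + 2 = 8; D2 = 54 − 42 + 2 = 14.
- C17D1 (week 48): D1 = 54 − 48 + 2 = 8; D2 = 66 − 48 + 2 = 20.
- C19D1 (week 54): D1 = 66 − 54 + 2 = 14; D2 = 78 − 54 + 2 = 26.

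| Visit | D2 from schedule | D2 from week limits in Rules 1–3 | D2 from exception | D2 from visit labels in the rules |
|---|---|---|---|---|
| C15D1 | 14 | 14 | 20 | 14 (Rule 1) or 20 (Rule 2) |
| C17D1 | 20 | 20 | 20 | 20 (Rule 2) or 26 (Rule 3) |
| C19D1 | 26 | 26 | 20 | not named |

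The exception is right for one of its three visits. The week limits are right for all three.

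**Effect at C19D1.** LATA at week 54, week-66 scan missed, progression at the week-78 scan: gap 78 − 54 = 24 weeks, one missed scan. With D2 = 26 this is an event; with D2 = 20 it is censored at week 54, against Table 2-6. For in-window dates (LATA 53 to 55, progression 77 to 79) the gap runs from 77 − 55 = 22 to 79 − 53 = 26 weeks, so every such case changes status.

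**Effect at C15D1.** An in-window week-54 scan is at most 55 − 41 = 14 weeks after LATA, so it is an event under both readings. An in-window week-66 scan is at least 65 − 43 = 22 weeks out, so it is censored under both. Only a death or unscheduled progression in between can change. Example: scans 48 and 54 missed and death at week 60, gap 60 − 42 = 18. This is censored with D2 = 14 but kept with D2 = 20, against Table 2-6.

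**Effect of Rule 3's label at C17D1.** An in-window week-66 scan is at most 67 − 47 = 20 weeks out and a week-78 scan at least 77 − 49 = 28, so again only off-schedule events can change. Example: scans 54 and 66 missed and death at week 72, gap 72 − 48 = 24. This is censored with D2 = 20 and kept with 26.

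**Censoring reasons.** LATA at week 54, no event, cut-off at week 77: gap 77 − 54 = 23. With D2 = 26 the reason is ongoing without event. With D2 = 20 it defaults to the category for adequate assessments having lapsed.

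**DOR.** SAP 2.7.4 has its own rule of two intervals plus two windows and does not mention the change of interval at week 54. With the 6-week interval this gives 2 × 6 + 2 = 14 at C17D1. A week-48 LATA, missed week-54 scan and progression at week 66 (gap 18, one missed scan) would then be censored, against Table 2-6.

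**The case against.** The strongest reply is that a usable rule is already there. SAP 4.5 says the limits depend on when the LATA falls. The week ranges (up to 45, after 45 to 51, after 51) are exclusive and exhaustive, match Table 5-4, and yield exactly the schedule-based values. A week-42 or week-54 LATA fails Rule 2's own condition even though the exception points there. Rule 1's label cannot be literal, because the rule covers every visit up to week 45. This stands to the extent that the intent can be inferred and the numbers need no change. It does not remove the contradiction: the exception is a complete, legible instruction keyed to visit names, and following it gives the wrong status.

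A reader might infer that DOR, a key secondary endpoint, is miscounted in the same way. The documents do not support that. SAP 4.5 is written for PFS, and SAP 2.8.1.4 (PFS) refers to it for counting missed scans. SAP 2.7.4 counts them for DOR without citing 4.5. Its statement that the same principles hold for PFS extends Table 2-6 from DOR to PFS; it does not bring 4.5 into DOR.

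The cut-off also limits the effect. The primary analysis is triggered when participants still on treatment have completed at least four assessments, approximately 24 weeks (SAP 1 and 2.1.1). The changes above need events from about week 42 + 14 = 56 at C15D1, and after week 54 + 20 = 74 at C19D1.

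**Conclusion.** The concern holds as a drafting error in the PFS missing-scan rule. The exception is wrong at C15D1 and C19D1, Rule 3 carries the wrong visit label, and Rule 2's description of its visit is inconsistent. The effect that matters is at C19D1, where an ordinary scheduled progression after one missed scan becomes a censored time 24 weeks earlier. It would be too strong to say that any event 14 to 20 weeks after a week-42 scan changes status: with in-window scans, this is confined to deaths and unscheduled progressions.

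PFS and its censoring-reason summary are exposed; ORR, the primary endpoint, is not. DOR is exposed only if 4.5 is applied to it, although its own text has a separate gap at week 54.

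The size rests on two conditions: the program follows the exception or the visit labels rather than the week limits, and participants have both missed scans and follow-up beyond about week 56 at the primary cut-off. The documents give no accrual timeline or missed-scan rate, so the number cannot be derived; it is probably small. This is a minor point, worth correcting because the fix is cheap.

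**What to change.** In SAP 4.5:

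- Restrict the D2 exception to C17D1. Do not simply delete it: the general definition would then give 2 × 6 + 2 = 14 or 2 × 12 + 2 = 26 weeks at C17D1, against Rule 2's 20.
- Label Rule 1 as matched visit C15D1 or earlier (LATA ≤ 45 weeks), Rule 2 as C17D1 (> 45 to ≤ 51 weeks) and Rule 3 as C19D1 or later (> 51 weeks).
- Keep D1/D2 at 8/14, 8/20 and 14/26 weeks.

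In SAP 2.7.4, refer to the corrected 4.5 so that DOR and PFS count missed scans in the same way.

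The cost is SAP wording and a check that the program matches it. Data collection, sample size and the primary analysis are unchanged.

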4.6 Patient reported outcomes

The text below gives more detailed instructions and rules needed for programming of the analyses described in [Section 2.11](#).

4.6.1 NSCLC-SAQ

The NSCLC-SAQ consists of seven items covering five domains:

- Cough
- Pain (2 items)
- Dyspnea
- Fatigue (2 items)
- Appetite

Items 1, 2 and 3 assess intensity and have response options of No <symptom> at all, Mild <symptom>, Moderate <symptom>, Severe <symptom>, and Very Severe <symptom>. Items 4 through 7 assess frequency and have response options of Never, Rarely, Sometimes, Often, and Always. The responses are coded as 0, 1, 2, 3, 4, where 0 corresponds to the lowest severity (no, never) and 4 corresponds to the highest (very severe, always).

The scoring algorithm of the NSCLC-SAQ total score is as follows:

- Cough score: score of the cough item, or missing if skipped
- Fatigue score: if both items present, compute mean; or use score from 1 item if the other is missing; or set to missing if both are skipped
- Pain score: if both items present, use most severe of both; or use score from 1 item if the other is missing; or set to missing if both are skipped
- Dyspnea score: score of the shortness of breath item, or missing if skipped
- Appetite score: score of the poor appetite item, or missing if skipped
- Total score: sum all five domain scores; if any are missing, a total score is not computed. This creates a total score ranging between 0 and 20 with higher scores indicating more severe symptomatology

